3.1 Main Objective

This study aims to establish a birth cohort to investigate the role of HIV and comorbidities on vertical HIV transmission, immune development and disease progression in children 0-2 years, HEU, HEI and HUU as the control group.

Objectives

A. All Mothers Regardless of HIV Status

- To determine the prevalence and incidence of coinfections (intestinal parasitic infections, HBV, HCV, CMV) malnutrition and non-communicable diseases (NCDs) (gestational diabetes mellitus, hypertensive disorders and CVD) risk factors over 24 months and relate all these comorbidities to:
 - a. Pregnancy outcome, infant growth, development, morbidity and mortality
 - b. Biomarkers of inflammation and immune activations

Infants

- 2. To determine vertically transmitted infections and incidence non-communicable diseases among infants.
- 3. To determine clinical and immunological profiles of HEI, HEU and HUU infants.

B. HIV+ Mothers: Chronic HIV infections

- 1. To determine vertical transmission rates of mothers with acute and chronic HIV infection on option B+
- 2. Determine any association(s) between different option B+ drug regimens, adverse pregnancy outcome, viral load suppression and CD4/CD8 counts on mothers and their infants

C. HIV+ Mothers; Acute HIV infections,

- 1. To determine the incidence of HIV in the postpartum period over the 2 years
- 2. To determine the viral set points, HIV suppression trends and biomarkers of immune activation
- 3. To determine the HIV and host genetic diversity and possible transmission linkages

Infants

To characterise natural killer cell phenotype and function longitudinally from cord blood at birth up to 2 years and relate to infant HIV acquisition , morbidity and mortality

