4.8 Mothers' Procedures

• A questionnaire will be administered at enrolment from which information regarding their sociodemographics, sexual behaviour and reproductive health issues including obstetrical records will be obtained. Antiretroviral use and regimen will be recorded for all the HIV+ mothers. Assessment of nutritional status/BMI will be done using standard anthropometric indices. A physical examination will be done at every visit by the study clinician. Mothers will be enrolled at 28-36 weeks gestation and followed up at delivery, 10 days and 6, 10, 14, 24, 36, 48, 72 and 96 weeks postpartum thus totaling 11 visits during the study period. Data can still be collected in cases of missed visits provided the participant turns up within the seven day window period of the scheduled visits. The participant may be asked to discontinue if she consecutively fails to turn up for at least two successive scheduled study visits without any reason(s).

Biological specimens blood, cord blood, amniotic fluid, breast milk urine and stool will be collected at different visit with the respective quantities and purposes as shown in the **Table** 1 below.

	Total Volume of Specimen Required						
Visit	HIV Status	Blood* (mL)	Stool** (grams)	Breast Milk* (mL)	Urine *** (mL)	Amniotic Fluid (mL)	Cord Blood (mL)
1	HIV+	30	20	-	100	50	
In Pregnancy	HIV-	25	20		100	50	
2 Delivery	HIV+	10	20		100	50	50
	HIV-	5	20		100	50	50
3 7 -10 days pp	HIV+	-	If delivery visit is	10	100		
	HIV-	-	missed some of the samples are collected.	10	100		
4 6 Weeks/1½Months pp	HIV+	20	20	10	100		
	HIV-	10	20	10	100	50	
5 10 Weeks /2½ Months	HIV+	20	20	10	100		
рр	HIV-	10	20	10	100		
6 14 Weeks, 3½Months	HIV+	20	20	10	100		
рр	HIV-	10	20	10	100		
7 24 Weeks/6 Months pp	HIV+	20	20	10	100		
	HIV-	10	20	10	100		
8 36 Weeks/9 Months pp	HIV+	20	20	10	100		
	HIV-	10	20	10	100		
9 48 Weeks/1 year	HIV+	20	20	10	100		
pp	HIV-	10	20	10	100		
10 72 Weeks /1 ^{1/2} years	HIV+	20	20	10	100		
	HIV-	10	20	10	100		
11 96 Weeks/2 years	HIV+	20	20	10	100		
	HIV-	10	20	10	100		

Table 1: Types and total Volumes of Maternal Specimen Required

*Generally blood samples, amniotic fluid cord blood and breast milk will be tested for trend in immune profiles and coinfections.

Stool samples will be tested for intestinal parasites * Urine

urinalysis

Procedure	Specimen	1	2	3	4	5	6	7	8	9	10	11

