/Test	Required	Volume/gra	labour	7-10 Day	6 wks	10 wks	14 wks	24 wks	36 wks	48 wks	72 wks	96 wks
	(volume)	m		рр	рр	рр	рр	рр	рр	рр	рр	рр
CMV / HBV/ HCV	serum(1 mL)	✓ (1
HIV testing/all negatives	Plasma (1 mL)	1	~	1	1	1	1	1	~	1	1	1
STI serology												
Parasites At least 3 specimens	Stool(10 g) Anal swab	1	1	1	1	1	1	1	1	1	1	1
FBC/Differentials/pla telets	Plasma (5mL)	√			1		1			1		1
Markers of immune	Blood (10mL)	1		✓	✓	✓	1	1	1	1	1	√
activation, cytokines levels and trends	Cord blood (10mL)		~									
	Amniotic fluid (10mL)		1									
	Breast milk(10 mL)			1	1	1	1	1	1	1	1	1
Urine	urinalysis	1			1			1				1
Biochemistry	Plasma (5 mL)	✓			1		1			1		1
Panel	Sugar (3 mL)	√			✓		1			1		✓
Restriction factors	Cord blood		✓									
	Breast milk			1	✓	✓	✓	1	✓	1	✓	✓
				FOR	HIV POSI	TIVES ONL	Y					
T cell profile	PBMCs	✓						1	✓	 ✓ 	1	 ✓
HIV RNA load*	Whole blood	√ *										
HLA/KIR host genetics												
HIV genetic diversity for Transmission linkages**	Whole blood	~										V

Table 2: Type, Volume, intervals of collection and Purpose of Maternal Specimens Required

*Re-testing with be done for all Unsuppressed HIV load every 3 months ** for all acute HIV infections

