4.10 Laboratory Methods

4.10.1 Sample Preparation and Storage

On the day of collection, clotted samples will be centrifuged for 5 minutes at 3000rpm. The supernatant will then be removed and placed in appropriately labelled serum cryo-tubes. All samples will be stored in the Department of Medical Laboratory Science at -70°C to -80°C for subsequent analysis.Full blood count, renal function, thyroid function, lipid profile, glucose levels, bone profile, and liver profile will be done at baseline, 6 weeks and thereafter every 6 months

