4.10.17 Transmission linkages

Mothers who seroconvert after enrolments will have host/viral genetics factors determined transmission linkages assessment. Peripheral blood mononuclear cells will be collected for these HUU, HEI and HEU infants for NK cell phenotype and functional analysis.

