4.10.17.1 Nucleic acid extraction and DNA Amplification

Total RNA was extracted from plasma using the NucliSENS isolation kit, based on the Boom *et al.*, method Briefly samples are lysed in a lysis buffer containing a chaotropic agent, guanidine thiocyanate. Cells, bacteria and viruses in the sample are lysed whilst proteins such as nucleases are denatured and inactivated. DNA and RNA bind to silica particles and everything else is washed following several washing steps with the wash buffer. Finally the nucleic acids are eluted from the silica particles using the elution buffer. Purified DNA will be stored at -80 for genotyping.*Taq* polymerase is a thermostable DNA polymerase named after the hot spring *Thermusaquaticus* bacterium. The primary PCR amplified an approximately 800-base pair (bp) fragment spanning the V3 and V4 region of the envelope (positions 6948–7537) on the HIV-HXB2 genome using HIV primers ENV 2 and NY3. Secondary or nested PCR amplified a 535-bp env gene fragment using a PCR Thermal cycler. Detection and quantification of secondary PCR amplicons were done using a 1% agarose gel electrophoresed together with a standard mass ladder and then stained with SYBR safe stain.

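### Table 2 marks viral sequencing for transmission linkage only at visit 1 and week 96 and ties no sequencing sample to a seroconverter's first HIV-positive visit

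*Protocol*

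**What the plan says.** The row in Table 2 (4.8) is labelled "HIV genetic diversity for Transmission linkages". It names whole blood as the specimen and carries two marks, one in the visit 1 column (pregnancy) and one in the visit 11 column (week 96). Its footnote reads "for all acute HIV infections" and gives no timing.

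Section 4.10.17 states who is assessed: "Mothers who seroconvert after enrolments will have host/viral genetics factors determined transmission linkages assessment". The purpose is objective C3 in section 3.1, under acute infections: "To determine the HIV and host genetic diversity and possible transmission linkages". Linkage of acute infections is also a research outcome in 4.10.24.

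Detection of seroconversion is scheduled closely. The Table 2 row "HIV testing/all negatives" is marked at all 11 visits. After enrolment at 28-36 weeks of gestation, mothers are "followed up at delivery, 10 days and 6, 10, 14, 24, 36, 48, 72 and 96 weeks postpartum".

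On specimens, 4.10.1 says: "All samples will be stored in the Department of Medical Laboratory Science at -70°C to -80°C for subsequent analysis". Section 4.10.17.1 says "Total RNA was extracted from plasma using the NucliSENS isolation kit", and later in the same paragraph that purified DNA is kept frozen for genotyping.

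**The concern.** A woman who seroconverts after enrolment has, by definition, a negative HIV test at visit 1. One of the two marks on the row therefore precedes her detected infection. The other is fixed at the last visit, whenever she was infected. Read as written, the schedule does not call for sequencing at the visit where a new infection is found.

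Linkage aims to relate the virus in a newly infected woman to its source and, where relevant, to her infant. The protocol's own background (1.10) treats rising within-host diversity over time as important for linkage, so a sample taken long after infection suits objective C3 less well than one taken at first detection. The number of cases will be small, and an early sample that was not set aside cannot be collected afterwards.

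**Working it through.** The protocol states no figure for this delay, so there is nothing to reproduce. The check has two parts.

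**1. Position of the marks.** Counting columns across the row gives marks in columns 1 and 11 and none in columns 2 to 10. Other rows of Table 2 are damaged in the text version (the CMV/HBV/HCV row has lost columns), but this one reads cleanly.

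**2. Who is affected and for how long.** Inputs from the protocol are enrolment at 28-36 weeks, the visits listed in 4.8, and an HIV test of negative women at each visit. The assumptions are delivery at 40 weeks, a constant hazard of infection from enrolment to week 96, every visit attended, and infection detected at the next scheduled test.

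The share first detected at a visit is the length of the interval before it divided by total time at risk. The last interval (week 72 to 96) is 24 weeks.

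| Enrolment (weeks) | Time at risk (weeks) | First positive at week 96 | First positive at visits 2-10 |
|---|---|---|---|
| 28 | 12 + 96 = 108 | 24/108 = 22.2% | 77.8% |
| 32 | 8 + 96 = 104 | 24/104 = 23.1% | 76.9% |
| 36 | 4 + 96 = 100 | 24/100 = 24.0% | 76.0% |

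For women first positive at visits 2-10, the wait to the only remaining mark is 96 minus the detection week. It runs from 24 weeks (detected at week 72) to 96 weeks (detected at delivery). The mean for enrolment at 32 weeks is the sum of interval length × wait, divided by 80 weeks:

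- Delivery: 8 × 96 = 768
- Day 10 (1.43 weeks): 1.43 × 94.57 = 135.2
- Week 6: 4.57 × 90 = 411.3
- Week 10: 4 × 86 = 344
- Week 14: 4 × 82 = 328
- Week 24: 10 × 72 = 720
- Week 36: 12 × 60 = 720
- Week 48: 12 × 48 = 576
- Week 72: 24 × 24 = 576

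The sum is 4578.5, and 4578.5/80 = 57.2 weeks.

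**Number of women.** Section 4.10.18 assumes 3% incidence without a time unit. With 600 HIV-negative women and no losses:

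- 3% cumulative: 600 × 0.03 = 18 seroconverters, of whom about 14 (18 × 0.769 = 13.8) are first positive at visits 2-10.
- 3% per year, enrolment at 32 weeks: 600 × (1 − 0.97²) = 35.5, of whom about 27 (35.5 × 0.769). Across enrolment at 28-36 weeks this is 34-37 seroconverters, of whom 26-29 are first positive at visits 2-10.

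**The case against.** The strongest reply is that material from the seroconversion visit is collected anyway. Table 2 allots plasma for HIV testing at all 11 visits and 10 mL of blood for immune markers at visit 1 and visits 3-11, and 4.10.1 freezes all samples. On this view only a stated trigger is missing. Much of that stands, and a reader who infers that the virus at seroconversion is never sampled goes too far: women first positive at week 96 are covered, and stored specimens may cover others. But storage does not secure the sample:

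- 4.10.1 describes clotted blood going into serum tubes, whereas 4.10.17.1 uses plasma.
- 4.10.8 runs the maternal tests on whole blood.
- Table 1 gives HIV-negative women 5 mL at delivery, none at 7-10 days and 10 mL at week 10. At week 10, Table 2 already lists 10 mL for immune markers plus 1 mL for the HIV test.

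A second reply is that the footnote and 4.10.17 can be read as event-driven, and that fixed columns cannot be the whole schedule. The viral load row, also marked only at visit 1, has a three-monthly re-test in its footnote. Figure 1 has a key entry for acute infections only, and the figure was not available here. This is possible, but the sequencing footnote gives no such timing, and the table should agree with any trigger stated elsewhere.

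A third is that the visit 1 mark may catch a woman recently infected at enrolment, since 4.10.8 relies on antibody tests. That stands for a minority, so the visit 1 specimen cannot be called empty of virus in every case. It does not fit the women 4.10.17 describes.

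A reader might also infer that treatment will leave nothing to amplify at week 96, or that linkage will be falsely rejected. The documents do not show either. Table 2 names whole blood and 4.10.17.1 mentions stored DNA, so a low plasma load need not prevent a sequence. The 40 copies/mL limit in 4.10.9 belongs to the viral load assay. No treatment start time or suppression rate is given for seroconverters. The six-month observation in 1.10 concerns infant sequence length, and 1.10 also reports studies with no clear trend.

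For infants, Table 4 already has a sub-heading keyed to the first positive sample. What remains there is a mismatch with the single mark at 96 weeks, in a table whose columns are partly damaged.

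**Conclusion.** The point holds as a scheduling fault. Table 2 fixes sequencing at visit 1 and week 96, the women concerned are those who seroconvert in between, and nothing ties a sequencing sample to their first positive visit. Under a constant hazard, delivery at 40 weeks and full attendance, 76-78% of seroconverters wait at least 24 weeks after first detection for the only usable mark, with a mean near 57 weeks for enrolment at 32 weeks. Missed visits would change these figures. That is roughly 14 women if the 3% is cumulative, or 26-29 if it is yearly, before losses.

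Severity is moderate. The schedule serves objective C3 and a listed research outcome poorly, but stored material may rescue some cases, and the linkage objective is not named among the five primary objectives in the protocol summary.

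**What to change.** - **Table 2:** for seroconverters, replace the visit 1 mark on the sequencing row with the first HIV-positive visit. Reserve an aliquot from blood drawn at that visit, or at the next visit with a blood draw where Table 1 allots none. Keep week 96 as a second sample. Check that Figure 1 agrees.
- **Table 4:** reconcile the 96-week mark on the infant linkage row with the sub-heading that refers to the first positive sample.
- **Specimen:** reconcile whole blood in Table 2 with 4.10.17.1, which refers both to RNA from plasma and to stored DNA for genotyping, and make 4.10.1 store whichever is chosen.

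Sampling should fit around care and should not alter treatment timing. The cost is small: one reserved aliquot per case and a check against the Table 1 blood volumes. There are still at most two sequences per woman, because the visit 1 sample is replaced rather than added to.

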4.9 Infants Procedures

From delivery infections, immunological profiles, co-infections patterns and trends, mortality will be determined and , feeding practices development , responses to standard vaccines, general health will be assessed. Types of specimen required and the test to be assayed are shown in **Tables 3 and 4**.

		Specimen Required							
Visits	Baby Status	Blood*	Stool**	Urine***	PBMCs****	1			
1	HIV+								
	HIV-								
2	HIV+								
	HIV-								
3	HIV+								
	HIV-								
4	HIV+								
	HIV-								
5	HIV+								
	HIV-								
6	HIV+								
	HIV-								
7	HIV+								
	HIV-								
8	HIV+								
	HIV-								
9	HIV+								
	HIV-								
10	HIV+								
	HIV-								
11	HIV+								
	HIV-								

Table 3: Types and total Volumes of Inf	fant Specimen Required
---	------------------------

*Generally blood samples will be tested for trend in immune profiles and coinfections.

**Stool samples will be tested for intestinal parasites

^{***} Urine for urinalysis

^{****}PBMC of infants born from mothers with acute HIV infection for NK cell phenotyping

Procedure	Specimen	1	2	3	4	5	6	7	8	9	10	
/Test	Required	Delivery	7-10 Day	6 wks	10 wks	14 wks	24 wks	36 wks	48 wks	72 wks	96 wks	
	(volume)		рр	pp V	рр	рр	рр	рр	рр	рр	рр	
CMV / HBV/ HCV	Sesement(1m)L)	• 🖌 (¥	Ť							~	1
HIV testing/all exposed infants	Plasma (2 mL)	~	1	1	~	1	1	1	1	1	1	
Parasites	Stool (5 grams)	1	1	~	1	1	1	1	1	1	1	
FBC/Differentials		~		✓		✓			1		✓	
Markers of immune activation, cytokines levels and trends	Blood,	1	1	1	1	1	1	1	1	*	1	
Urine dip stick	Urine (5 ml)		1						1		1	
Biochemistry	ALT, AST, albumin,		1	1		1			1		1	
	Sugar		1	✓		✓			1		✓	
			PMBC for int	fants born f	rom Mothers	with acute H	IV infections					
		HE	Infants only o	on First HI	V positive sar	nple, thereaft	er every 3 mor	nths				
T cell profile	Whole blood		1	1	~	~	1	~	1	~	1	
HIV RNA load*	Whole blood											1
HIV genetic diversity for Transmission	Whole blood										V]
linkages**												

Table 4: Type, Volume, intervals of collection and Purpose of Infant Specimens Required

All the tests will be done locally except for transmission linkages assay and NK cell phenotyping that will be done in South Africa.

4.10 Laboratory Methods

4.10.1 Sample Preparation and Storage

On the day of collection, clotted samples will be centrifuged for 5 minutes at 3000rpm. The supernatant will then be removed and placed in appropriately labelled serum cryo-tubes. All samples will be stored in the Department of Medical Laboratory Science at -70°C to -80°C for subsequent analysis.Full blood count, renal function, thyroid function, lipid profile, glucose levels, bone profile, and liver profile will be done at baseline, 6 weeks and thereafter every 6 months

4.10.2 Determination of Full Blood Count (FBC)

FBC report of white blood counts (WBC) and differentialswill give an idea about the presence of anaemia, infection, inflammation or blood disorders. Peripheral blood for FBC analysis will be sent to the laboratory in an EDTA tube and analysed using a Mindray Haematology Analyser, BC3600within six hours of collection. Results will be grouped into white and red cell parameters including platelets

4.10.2.1 White Blood Cells Parameters

The FBC provides a total white cell count (WCC x 10^9)/white blood cell count (WBC) and an automated differential WCC which typically includes information the absolute and % of each type of white cell about neutrophils, lymphocytes, monocytes, eosinophils and basophils.

4.10.2.2Red Blood Cells Parameters

Iron deficiency anaemia will determined according to WHO guidelines where haemoglobin (Hb) level below 11gm/dl in pregnant women constitutes anaemia with haemoglobin below 7gm/dl indicating severe anaemia. Iron deficiency anaemia is suspected if the red cells show a *microcytic hypochromic* classification. An mean corpuscular volume (MCV) between 80 and 97 fL is normocytic, above 97 fl

is macrocytic and below 80 fl is microcytic. An mean corpuscular haemoglobin concentration (MCHC) between 31 and 34% is normochromic, above 36% is hyperchromic and below 31%, it is hypochromic. A diagnostic postpartum Hb level 10.0 g/dLwill be used.

4.10.2.3Platelet Counts

Gestational thrombocytopenia will be defined as a platelet count of less than 150 x 10 3 µL in hypertensive pregnant women during the third trimester. Platelet count of <100 000 µL will be an indicator of increased chance of pre-eclampsia in hypertensive pregnant women during the third trimester.

4.10.3 Biochemistry Determination 4.10.3.1Blood Glucose Determination

Blood will be collected in grey topped tubes (potassium oxalate and sodium fluoride) for HbA1C analysis and random blood glucose levels. A cutoff value of 6.5% will identify undiagnosed diabetes whilst individuals with A1C \geq 5.6% will be assumed to have an increased risk for future diabetes according to the Glycohemoglobin standardization guidelines. The glucose levels will be analysed on Mindray BS200 Chemistry Analyser. All the blood tests will be conducted at Immuno-Path Diagnostic Laboratory Services.

4.10.3.2Kidney Function Profiles

Urea and electrolytes, essentially sodium and potassium including lactate dehydrogenase, will be done on mothers' and infants' serum or plasma samples baseline, 10 days, six weeks and every 6 months postpartum.

4.10.3.3Liver function Profiles

Albumin, bilirubin, hepatic enzymes; alanine transaminase (ALT), specific to the liver and aspartate transaminase more widely distributed are markers of damage to cells. Alkaline phosphatase (ALP) and gamma glutamyl transpeptidase (GGT) are markers of cholestasis.

4.10.3.4Lipid profiles

Risk factors of CVDs of borderline and high risk ranges for cholesterol, triglycerides, high-density lipoprotein cholesterol (HDLc), low-density lipoprotein cholesterol (LDLc) cholesterol and cholesterol/HDL ratio at baseline will be determined using Mindray BS120 automated analyserat baseline, 10 days, six weeks and every 6 months postpartum.

4.10.3.5Bone Profiles

Longitudinal changes in ionised calcium, phosphorus, albumin and alkaline phosphatase levels in pregnancy (baseline), lactation (10 days pp, six weeks, 6 months) and weaning (earliest visit then after 6 months).Serum parathyroid hormone (PTH) including serum 1,25 (OH)₂ Vitamin D level will be
determined at baseline, 6 weeks, 6, 12 and 24 months postpartum. <25 nmol/L will be the cut off value for 25-OH Vitamin D deficient.

4.10.4 Determination of Serum prolactin Levels

Serum prolactin levels in pregnancy, 7-10 day pp, 6 weeks and thereafter 6 monthly will be determined using Sandwich (quantitative) Abcam^R. Prolactin Human ELISA Kit (ab108655) according to the manufacturer's instruction. The serum concentration of prolactin will be given in ng/mL which will be correlated with the reported breastfeeding patterns and frequencies.

4.10.5 Determination of Coinfections

HBs Ag/anti-HB/anti-HCV/anti-CMV will be screened at enrolment and at 24 month postpartum for the mothers using qualitative rapid immunochromatographic assays. These will coinfections will be tested in the peripheral blood, cord blood including amniotic fluid. Stool specimen will be examined for intestinal parasitic infections at the age of 7-10 days and six weeks old for the infants.

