4.0 Methodology

4.1 Study Design

A prospective cohort study of 1200 pregnant women (600 HIV positive and 600 HIV negative). **Figure 1** below is the study flow diagram.

Viral load re-testing with be done for all Unsuppressed HIV load every 3 months

Figure 1: Study Flow Diagram

Key

*Pregnancy outcome include spontaneous abortions, birth defects, multiple births, low birth weights preterm infants, birth with prolonged hospitalization, birth requiring neonatal intensive care, maternal, perinatal and infant deaths.

**Coinfections include HBV, HCV, CMV and intestinal parasites

***NCD, non-communicable diseases (hypertensive disorders, malnutrition, diabetes)

**** For acute HIV infections ONLY

*****Adverse feotal outcomes include preterm birth (<37 weeks of gestation) low Apgar score<7, low birth weight, Fetal macrosomia, birth weight of more than 4,000 grams, birth defects, stillbirth (death of a fetus weighing \geq 500g or \geq 22 weeks gestation if weight is unavailable), early neonatal death (death between 0-6 days of life), neonatal death (death within the first 28 days of life), neonatal jaundice, infant death, intensive care unit admission, hospital admissions including documented local clinic treatments

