4.10.18 Sample Size Determination

Pocock's formula was used to determine sample size (n) required:

- $n = \frac{p_1(1-p_1)+p_2(1-p_2)(Z_{\alpha}-Z_{\beta})^2}{(p_1-p_2)^2}$
- Where p_1 and p_2 are proportion of success in population 1 and 2
- Z_{α} and Z_{β} are values of standard normal distribution
- α = Significance level
- $\beta = Power$

3% incidence rate has been assumed to factor in for the a high risk of vertical transmission in the breastfeeding period for the few anticipated acute HIV infection²³⁴.With the advent of cell phones the % loss to follow up may not be that bad and cannot be similar for the first and second year. Factored in the worst case scenario of a 15% and 20% loss to follow-up during the first and second year respectively, a minimum sample size required computed using **STATA** is 1200 (600 HIV+ and 600 HIV-) mothers. Assuming a 15% and 20% loss to follow up in the first and second year of the study respectively, should leave us with at least the 417 infants. The sample size has power to predict diseases outcomes of HEU children which must culminate in their improved management. The sample size has not factored in sample sizes of sub-studies linked to it in the **Appendices' Section 6.2**. Should there be sub-studies, they should fit within this parent protocol. These aim to address all the research gaps highlight throughout the literature review.

	a) HIV Chronic Infection		b) HIV Acute Infection	c) HIV Negative	Outcomes
Comorbidities	Treatment experienced Immune	Treatment naive Profiles for dif	ferent comorbidities c	ombinations	Prevalence and incidence of comorbidities, comorbidities trends relating comorbidities to
HBV HCV CMV					immunological profiles, pregnancy outcomes, vertical transmission of infections, patterns and
Anaemia Diabetes Nutritional Status					transmission linkages, infant/child growth and neurodevelopment
Hypertensive disorders					

Table 5: Pictorial Depiction of the Stratification

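### Maternal HBV, HCV and CMV tests are dated only at enrolment and 24 months, with none set for women who leave earlier, although incidence over 24 months is a primary objective

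*Protocol*

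**What the plan says.** - **Objective.** Section 3.1, objective A1, is "To determine the prevalence and incidence of coinfections (intestinal parasitic infections, HBV, HCV, CMV", among other conditions, over 24 months. The results are to be related to infant growth, development, morbidity and mortality. The Protocol Summary lists incidence of co-infections under the primary objectives and incidence of comorbidities under the primary end points.
- **Test dates.** Section 4.10.5: "HBs Ag/anti-HB/anti-HCV/anti-CMV will be screened at enrolment and at 24 month postpartum for the mothers using qualitative rapid immunochromatographic assays". It gives no rule for early exit. By contrast, Table 2 has HIV-negative mothers retested for HIV at every visit.
- **Cohort and losses.** Section 4.1: "A prospective cohort study of 1200 pregnant women (600 HIV positive and 600 HIV negative" women. Section 4.10.18: "Factored in the worst case scenario of a 15% and 20% loss to follow-up during the first and second year respectively".
- **Ways of leaving.** Section 4.8 allows discontinuation after two successive missed visits. Section 4.10.19 ends a mother's participation if her child dies.
- **Stored material.** Table 1 has maternal blood drawn at delivery and at each visit from 6 to 96 weeks. Section 4.10.1: "All samples will be stored in the Department of Medical Laboratory Science at -70°C to -80°C for subsequent analysis". Section 4.10.19 seeks consent to keep the specimens and use them later.

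**The concern.** The second test is tied to a calendar date and not to the end of each woman's follow-up. A woman who attends for a year and a half and then leaves has an enrolment result and nothing dated after delivery, so she contributes neither an event nor time at risk. Incidence, and its comparison between HIV-positive and HIV-negative mothers, then rests on those who reach 96 weeks.

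The child-death rule makes this more than a loss of numbers. If an infant dies before 24 months, the mother has no dated postpartum result. A maternal infection acquired after enrolment therefore cannot be linked to that death through this test, although objective A1 asks for such a link.

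For women who are newly positive at 24 months, the infection is dated only to a window of about two years. It cannot be placed before or after an infant event within that window.

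**Working it through.** **1. The plan's own retention figure.** Section 4.10.18 says the losses "should leave us with at least the 417 infants". Starting from 600 in one HIV group:

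- losses in sequence: 600 × 0.85 × 0.80 = 408, which is 9 below 417 (9/417 = 2.2%);
- losses added: 600 × (1 − 0.35) = 390.

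Sequential loss comes close to the stated figure, so it is the main case. Added loss is the alternative.

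**2. Women without a dated postpartum result.**

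- In sequence: year 1, 1200 × 0.15 = 180; year 2, 1020 × 0.20 = 204; total 384 (32%), leaving 816.
- Added: 180 + 240 = 420 (35%), leaving 780.

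**3. How many of these were at risk.** Only women negative at enrolment can have a new infection. The protocol gives no prevalence for this population. The figures cited in sections 1.4 and 1.4.1 come from elsewhere and serve here as assumptions (sequential loss):

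| Virus | Assumed prevalence | Negative at enrolment | Of these, no second result (× 0.32) |
|---|---|---|---|
| HBV | 5% | 1140 | 365 |
| HCV | 3% | 1164 | 372 |
| CMV | 84% to 100% | 192 to 0 | 61 to 0 |

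**4. Time that stored blood could recover.** Assume that loss is uniform within each 48-week year, that the last sample comes from the last attended visit with a blood draw (delivery, 6, 10, 14, 24, 36, 48, 72 weeks), and that time is counted from delivery.

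- Year-1 leavers, mean last draw: (6×0 + 4×6 + 4×10 + 10×14 + 12×24 + 12×36)/48 = 924/48 = 19.25 weeks.
- Year-2 leavers: (24×48 + 24×72)/48 = 60 weeks.
- Recovered, in sequence: (180 × 19.25 + 204 × 60)/52 = about 302 person-years. Completers give 816 × 96/52 = about 1506, so the gain is 20%.
- Recovered, added: (180 × 19.25 + 240 × 60)/52 = about 344, against 780 × 96/52 = 1440, a gain of 24%.
- Year-1 leavers with no blood after delivery: 6/48, or 1 in 8.

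These totals count all leavers. If leaving is unrelated to enrolment status, the 302 becomes about 287 for HBV (× 0.95), 293 for HCV (× 0.97) and 0 to 48 for CMV (× 0 to 0.16).

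**5. What completer-only data do to cumulative incidence.** Let r be the risk in leavers divided by the risk in completers. Completer estimate divided by whole-cohort value = 1/(0.68 + 0.32r). The documents give no value of r, so these values are illustrative only:

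| r | 32% lost | 35% lost |
|---|---|---|
| 1 | 1.00 | 1.00 |
| 1.5 | 0.86 | 0.85 |
| 2 | 0.76 | 0.74 |
| 3 | 0.61 | 0.59 |

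A ratio below 1 would move the estimate the other way.

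**The case against.** - **Other tests might fill the gap.** Section 4.10.5 goes on to name cord blood and amniotic fluid, and the Table 1 footnote speaks of testing samples for trends in coinfections. It would therefore be too strong to say that early leavers have no further result of any kind. However, the section sets no later date for those fluids, which as delivery specimens would give no later postpartum result, and the footnote sets no dates. The CMV/HBV/HCV row of Table 2 is not fully legible in the text used here. If the original shows ticks between enrolment and week 96, it contradicts section 4.10.5 and the two must be reconciled.
- **The losses are a worst case.** This stands. Section 4.10.18 itself expects that loss may be milder, so 384 is a planning bound and not a forecast.
- **Bias is not shown.** This stands. A reader might infer that incidence will be understated by some stated percentage. The documents do not support that, because any such figure comes entirely from an assumed r, and r = 1 gives no bias. The child-death rule makes a difference plausible but does not size it.
- **Not all 1200 women are at risk.** This stands, above all for CMV. The number of missed events is also unknown: the only incidence assumption ("3% incidence rate has been assumed") concerns HIV.
- **Early leavers can be left to the analysis plan.** Only in part. Censoring rules can be set there, but the choice of specimens to assay is made in this protocol, and no analysis can use results that were never produced. Storage and consent permit the extra tests, but nothing requires them.
- **Timing.** Infections already present at enrolment are correctly placed before delivery. Only later infections are undated.

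**Conclusion.** The point holds in a limited form. As written, section 4.10.5 gives women who leave before 24 months no dated postpartum result for infections whose incidence over 24 months is a primary objective. Under the worst-case losses this affects about 384 of 1200 women (32%), or 420 (35%) if the losses are added. Fewer of them are at risk once women positive at enrolment are set aside, and for CMV possibly very few.

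The missing results are partly tied to infant mortality through the child-death rule. Precision is lost in any case. Whether there is bias, and in which direction, cannot be determined from the protocol.

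Stored blood fills part of the gap and not all of it: roughly 300 person-years under uniform loss, and only up to each woman's last draw. It would be wrong to infer that storage restores complete follow-up.

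**What to change.** Amend section 4.10.5 along these lines:

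- *For a woman negative at enrolment, the second HBV, HCV and CMV test is done at 24 months or, if she leaves earlier, on her last stored serum or plasma sample.*
- *For each newly positive woman, the intermediate stored samples are tested to narrow the date of infection.*
- *Incidence is calculated for each virus among women negative at enrolment. Time at risk runs to the last negative sample for those who stay negative and to the estimated infection date for those who convert (the midpoint between last negative and first positive sample, or interval-censored methods).*

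The time-at-risk wording matters. Counting every woman to her last tested sample would include time after infection, and leaving out the enrolment condition would put women in the denominator who cannot convert. With intermediate samples tested, the postpartum dating window falls from about two years to the gap between draws, which is 4 to 24 weeks on the visit schedule.

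**Cost.** No new visit or blood draw is needed. A second test for all 1200 women is already implied by the schedule, so early leavers add none to that total. The extra tests are those on intermediate samples of newly positive women. Three conditions need checking: the rapid assays must be suitable for frozen samples; enough volume must remain after the other assays (Table 2 lists 1 mL of serum for this one); and second-round kits must be funded, since section 4.10.23 describes the current budget as covering the baseline surveys.
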